9.3 Clinical Study Report and Publications

A Signatory Investigator must be selected to sign the clinical study report.

For this protocol, the Signatory Investigator will be selected as appropriate based on the following criteria:

- Study Steering Committee chair or their designee
- Subject recruitment (eg, among the top quartile of enrollers)
- Involvement in trial design

The data collected during this study are confidential and proprietary to BMS. Any publications or abstracts arising from this study must adhere to the publication requirements set forth in the clinical trial agreement (CTA) governing [Study site or Investigator] participation in the study. These requirements include, but are not limited to, submitting proposed publications to BMS at the earliest practicable time prior to submission or presentation and otherwise within the time period set forth in the CTA.

10 GLOSSARY OF TERMS

Term	Definition
Complete Abstinence	
Complete Abstinence is defined as complete avoidance of heterosexual intercourse and is an acceptable form of contraception for all study drugs. This also means that abstinence is the preferred and usual lifestyle of the patient.
 
This does not mean periodic abstinence (eg, calendar, ovulation, symptothermal, profession of abstinence for entry into a clinical trial, post-ovulation methods) and withdrawal, which are not acceptable methods of contraception. Women must continue to have pregnancy tests. Acceptable alternate methods of highly or less effective contraception's must be discussed in the event that the subject chooses to forego complete abstinence.

Renal Responder	
Renal responders are defined as subjects who achieve a reduction of their baseline UPCR of $\geq 50\%$ and to less than 3 with no worsening of baseline estimated glomerular filtration rate (eGFR: normal or $\geq 75\%$ baseline if below normal at baseline).

11 LIST OF ABBREVIATIONS

Term	Definition
ACEi	angiotensin-converting-enzyme inhibitor
ACTH	adrenocorticotrophic hormone
AE	adverse event
aGVHD	Acute graft-versus-host disease
ALT	alanine aminotransferase
ARB	angiotensin receptor blocker
AST	aspartate aminotransferase
AUC	area under the concentration-time curve
β-HCG	beta-human chorionic gonadotrophin
BMI	body mass index
BMS	Bristol-Myers Squibb
BP	blood pressure
BUN	blood urea nitrogen
C	Celsius
CBC	complete blood count
CDC ACIP	The Center for Disease Control Advisory Committee on Immunization Practices
CFR	Code of Federal Regulations
CHF	Congestive heart failure
CI	confidence interval
CKD-EPI	Chronic Kidney Disease - Epidemiology
Cl-	chloride
cm	centimeter
Cmax	Peak serum concentration of abatacept
Cmin	Trough level serum concentration of abatacept
CRF	Case Report Form, paper or electronic
CS	corticosteroids
CTA	Clinical trial agreement
CXR	Chest X-ray

Term	Definition
DB	Double-blind
DILI	Drug induced liver injury
dL	deciliter
DMC	Data Monitoring Committee
DNA	Deoxyribonucleic acid
D5W	5% Dextrose in Water
ECL	electrochemiluminescence
eCRF	Electronic Case Report Form
EDC	Electronic Data Capture
eg	exempli gratia (for example)
eGFR	Estimated glomerular filtration rate
EIA	enzyme immunoassay
ELISA	Enzyme-linked immunoabsorbent assay
EMRs/EHRs	electronic medical/health records
ER	Emergency room
ESRD	End stage renal disease
F	Fahrenheit
FDA	Food and Drug Administration
FSGS	Focal Segmental Glomerulosclerosis
FSH	follicle stimulating hormone
g	gram
GCP	Good Clinical Practice
GGT	gamma-glutamyl transferase
GFR	glomerular filtration rate
h	hour
HBsAg	hepatitis B surface antigen
HBV	hepatitis B virus
HCV	hepatitis C virus
Hgb	hemoglobin
HIPAA	Health Insurance Portability and Accountability Act

Term	Definition
HIV	Human Immunodeficiency Virus
HRT	hormone replacement therapy
hsCRP	High sensitivity C-reactive protein
HSDS	height standard deviation score
IB	Investigator Brochure
ICD	International Classification of Diseases
ICF	Informed consent
ICH	International Conference on Harmonisation
ie	id est (that is)
IEC	Independent Ethics Committee
IFN- γ	Interferon gamma release assay
Ig	immunoglobulin
IMP	investigational medicinal products
IND	Investigational New Drug Exemption
INH	isoniazid
IP	Investigational product
IRB	Institutional Review Board
ITT	Intent-to-Treat
IU	International Unit
IUD	Intrauterine device
IUS	Intrauterine-hormonal releasing system
IV	intravenous
kg	kilogram
JIA	Juvenile idiopathic arthritis
L	liter
LAM	lactation amenorrhea method
ln	natural logarithm
LN	Lupus nephritis
LPLV	Last patient last visit
MCD	Minimal Change Disease

Term	Definition
mg	milligram
min	minute
mL	milliliter
MMF	mycophenolate mofetil
mmHg	millimeters of mercury
MPA	mycophenolic acid
MTD	maximum tolerated dose
µg	microgram
N	number of subjects or observations
N/A	not applicable
ng	nanogram
Non-IMP	non-investigational medicinal product
NS	Nephrotic Syndrome
NSAID	nonsteroidal anti-inflammatory drug
NYHA	New York Heart Association
OLE	Open Label Extension
OR	Odds ratio
PA	posterioranterior
PD	pharmacodynamics
PEF	Peak expiratory flow
pJIA	Polyarticular juvenile idiopathic arthritis
PK	pharmacokinetics
PPD	Purified protein derivative
PROMIS	Patient Reported Outcomes Measurement Information System
RA	Rheumatoid arthritis
RAS	Renin-angiotensin system
RBC	red blood cell
RNA	Ribonucleic acid
SAE	serious adverse event
SD	standard deviation

Term	Definition
SLE	Systemic lupus erythematosus
SNPs	single nucleotide polymorphisms
SOP	Standard Operating Procedures
Subj	subject
t	temperature
T	time
TAO	Trial Access Online, the BMS implementation of an EDC capability
TB	tuberculosis
Tmax	Time to reach peak serum concentration of abatacept
TRNS	Treatment Resistant Nephrotic Syndrome
ULN	Upper limit normal
UPCR	Urine Protein to Creatinine Ratio
UR	urinary recovery
URI	Upper respiratory infections
WBC	white blood cell
WHO	World Health Organization
WOCBP	women of childbearing potential
Xu	Amount of abatacept excreted in urine

APPENDIX 1 CENTRAL PATHOLOGY REVIEW
CENTRAL PATHOLOGY REVIEW SOURCE DOCUMENT
FOCAL SEGMENTAL GLOMERULOSCLEROSIS

Page 1 of 2

Site #	Subject #	Date of Kidney Biopsy Report (DD-MMM-YYYY)	Date Sent to Central Reader (DD-MMM-YYYY)

Instructions: LM, IF/IHC, and EM are required to fulfill pathologic enrollment criteria for FSGS.

Check Response	Inclusion Criteria
 Yes  No	
 LM: Minimum sample requirement is 5 or more glomeruli for LM in the LM/IF/IHC/EM sections combined. At least one glomerulus in combined tissue for LM/IF/IHC/EM with segmental sclerosis (with or without hyalinosis) or consolidation described in the Columbia FSGS Classification System (excluding collapsing variant) or as described for infantile/childhood “diffuse mesangial sclerosis”. If yes, classify as:
	NOS variant
	Tip variant
	Perihilar variant
	Cellular variant
	“Diffuse mesangial sclerosis” using CureGN criteria
	Indeterminate (insufficient for confident classification)
 Yes  No	
 IF/IHC: <1+ glomerular staining for IgG and IgA; and ≤ 1+ glomerular IgM, C3 and C1q (on a scale of 0-3 or 0-4) (except in areas of hyalinosis or sclerosis). Note: >1+ staining for C1q reflexes case to C1qN enrollment.
 Yes  No	
 EM: Absence of immune complex-type electron dense deposits other than small segmental mesangial dense deposits (except in cases reflexed to C1qN).

CENTRAL PATHOLOGY REVIEW SOURCE DOCUMENT
FOCAL SEGMENTAL GLOMERULOSCLEROSIS

Page 2 of 2

Check Response	Exclusion Criteria:
 Yes  No	
 • LM/IF/IHC/EM findings indicative of other glomerular disease [including collapsing FSGS (collapsing glomerulopathy)]
 Yes  No	
 • IF/IHC: $\geq 1+$ glomerular staining for IgG and IgA, and $>1+$ glomerular IgM, C3 and C1q (on a scale of 0-3 or 0-4) (except in areas of hyalinosis or sclerosis). Note: $>1+$ staining for C1q reflexes case to C1qN enrollment.
 Yes  No	
 • EM: Widespread well-defined immune complex-type electron dense deposits (except in cases reflexed to C1qN).
	Non-Excluding Pathology Findings:
—	
 • LM: Mild mesangial hypercellularity or concurrent features of arterionephrosclerosis.
Check Response	Assessment of Central Pathology Reader
 Yes  No	
 • Pathology entry criteria for FSGS fulfilled 
Date of Assessment (DD-MMM-YYYY) _____
 
Assessor Initials: _____

—	
 • Reflexed to C1q nephropathy

CENTRAL PATHOLOGY REVIEW SOURCE DOCUMENT

MINIMAL CHANGE DISEASE

Page 1 of 2

Site #	Subject #	Date of Kidney Biopsy Report (DD-MMM-YYYY)	Date Sent to Central Reader (DD-MMM-YYYY)

Instructions: LM, IF/IHC and EM are required to fulfill pathologic enrollment criteria for MCD.

Check Response	Inclusion Criteria
 Yes  No	
 LM: Ten or more nonsclerotic glomeruli must be available for examination in LM/IF/IHC/EM. Histologically unremarkable glomeruli except for mesangial hypercellularity and globally sclerotic obsolescent glomeruli. Note: Any amount of mesangial hypercellularity will be allowed and scored later
 Yes  No	
 IF/IHC: <1+ glomerular staining for IgG and IgA and ≤ 1+ glomerular C3 and C1q (on a scale of 0-3 or 0-4). Any intensity of IgM staining is allowed and the intensity scored later. Note: >1+ staining for C1q reflexes case to C1qN enrollment.
 Yes  No	
 EM: Absence of immune complex-type electron dense deposits (except in cases reflexed to C1qN). Any degree of foot process effacement is allowed, however, if there is minimal or no foot process effacement, clinical/laboratory features must strongly support a diagnosis of MCD in the patient (e.g. substantial proteinuria at some point in the course of disease).
Check Response	Exclusion Criteria:
 Yes  No	
 LM/IF/IHC/EM findings indicative of other glomerular disease.
 Yes  No	
 IF/IHC: ≥1+ glomerular staining for IgG, and IgA, and >1+ glomerular C3 or C1q (on a scale of 0-3 or 0-4). Note: >1+ staining for C1q reflexes case to C1qN enrollment.

CENTRAL PATHOLOGY REVIEW SOURCE DOCUMENT
MINIMAL CHANGE DISEASE

Page 2 of 2

Check Response	Exclusion Criteria
 Yes  No	
 EM: Immune complex-type electron dense deposits (except in cases reflexed to C1qN).
Check Response	Non-Excluding Pathology Findings:
—	
 LM: Globally sclerotic glomeruli, mild mesangial hypercellularity, or concurrent features of arterionephrosclerosis
Check Response	Assessment of Central Pathology Reader
 Yes  No	
 Pathology entry criteria for MCD fulfilled 
Date of Assessment (DD-MMM-YYYY) _____
 
Assessor Initials: _____

—	
 Reflexed to C1q nephropathy

CENTRAL PATHOLOGY REVIEW SOURCE DOCUMENT

C1q Nephropathy

Site #	Subject #	Date of Kidney Biopsy Report (DD-MMM-YYYY)	Date Sent to Central Reader (DD-MMM-YYYY)

Check Response	Inclusion Criteria:
__ MCD __ FSGS	
 LM: Light microscopic findings fulfilling CureGN criteria for minimal change disease or focal segmental glomerulosclerosis (excluding collapsing variant). If yes for FSGS, classify as follows:
__	NOS variant
__	Tip variant
__	Perihilar variant
__	Cellular variant
__	Indeterminate (insufficient for confident classification)
__ Yes __ No	
 IF/IHC: >1+ staining for C1q with any amount of staining for IgG, IgA, IgM and C3 (on a scale of 0-3 or 0-4).
__ Yes __ No	
 EM: Mesangial immune complex-type electron dense deposits with or without scattered subendothelial and subepithelial deposits.
Check Response	Exclusion Criteria:
__ Yes __ No	
 LM/IF/IHC/EM findings indicative of glomerular disease other than MCD or FSGS, especially lupus GN.

Check Response	Non-Excluding Pathology Findings:
—	
 • LM: Globally sclerotic glomeruli, mild mesangial hypercellularity or concurrent features of arterionephrosclerosis
Check Response	Assessment of Central Pathology Reader
— Yes	
 • Pathology entry criteria for C1qN fulfilled
— No	Date of Assessment (DD-MMM-YYYY) _____ Assessor Initials: _____

APPENDIX 2 METHODS OF CONTRACEPTION

At a minimum, subjects must agree to use one highly effective method of contraception as listed below:

HIGHLY EFFECTIVE METHODS OF CONTRACEPTION

Highly effective methods of contraception have a failure rate of < 1% when used consistently and correctly. WOCBP and female partners of male subjects, who are WOCBP, are expected to use one of the highly effective methods of contraception listed below. Male subjects must inform their female partners who are WOCBP of the contraceptive requirements of the protocol and are expected to adhere to using contraception with their partner. Contraception methods are as follows:

- 1) Progestogen only hormonal contraception associated with inhibition of ovulation.
- 2) Hormonal methods of contraception including oral contraceptive pills containing combined estrogen + progesterone, vaginal ring, injectables, implants and intrauterine devices (IUDs) such as Mirena®
- 3) Nonhormonal IUDs, such as ParaGard®
- 4) Bilateral tubal occlusion
- 5) Vasectomised partner with documented azoospermia 90 days after procedure
 - a) Vasectomised partner is a highly effective birth control method provided that partner is the sole sexual partner of the WOCBP trial participant and that the vasectomised partner has received medical assessment of the surgical success.
- 6) Intrauterine hormone-releasing system (IUS).
- 7) Complete abstinence
 - a) Complete abstinence is defined as the complete avoidance of heterosexual intercourse (refer to Glossary of Terms)
 - b) Complete abstinence is an acceptable form of contraception for all study drugs and must be used throughout the duration of the study treatment (plus 5 half-lives of the investigational drug plus 30 days).
 - c) It is not necessary to use any other method of contraception when complete abstinence is elected.
 - d) Subjects who choose complete abstinence must continue to have pregnancy tests, as specified in [Section 6.4](#).
 - e) Acceptable alternate methods of highly effective contraception must be discussed in the event that the subject chooses to forego complete abstinence.
 - f) The reliability of sexual abstinence needs to be evaluated in relation to the duration of the clinical trial and the preferred and usual lifestyle of the subject.

Local laws and regulations may require use of alternative and/or additional contraception methods.

UNACCEPTABLE METHODS OF CONTRACEPTION

- 1) Periodic abstinence (calendar, symptothermal, post-ovulation methods)
- 2) Withdrawal (coitus interruptus)
- 3) Spermicide only
- 4) Lactation amenorrhea method (LAM)

[REDACTED]

[REDACTED]

[REDACTED]

[REDACTED]

[REDACTED]

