- b) Women of childbearing potential (WOCBP) must have a negative serum or urine pregnancy test (minimum sensitivity 25 IU/L or equivalent units of HCG) within 24 hours prior to the start of study drug.
- c) Women must not be breastfeeding
- d) Women of childbearing potential (WOCBP) must agree to follow instructions for method(s) of contraception for the duration of treatment with study drug (abatacept/placebo) plus 5 half-lives (70 days) plus 30 days (duration of ovulatory cycle) for a total of 100 days post-treatment completion.
- e) Females who are not of childbearing potential must have documented proof that they are not of childbearing potential (eg, not experienced menarche, surgically sterile).
- f) Males who are sexually active with WOCBP must agree to follow instructions for method(s) of contraception for the duration of treatment with study drug (abatacept/placebo) plus 5 half-lives of the study drug (70 days) plus 90 days (duration of sperm turnover) for a total of 160 days post-treatment completion. In addition, male subjects must be willing to refrain from sperm donation during this time.
- g) Azoospermic males are exempt from contraceptive requirements. WOCBP who are continuously not heterosexually active are also exempt from contraceptive requirements and still must undergo pregnancy testing as described in this section.

Investigators shall counsel WOCBP, and male subjects who are sexually active with WOCBP, on the importance of pregnancy prevention and the implications of an unexpected pregnancy.

Investigators shall advise on the use of highly effective methods of contraception ([Appendix 2](#)) which have a failure rate of < 1% when used consistently and correctly.

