- Subjects who completed Period 1 and entered Period 2 prior to the protocol revision:
 - For subjects on abatacept during Period 1 and entering OLE period, it is the sum of the following:
 - ◆ Exposure in Period 1 = (date of first study medication in Period 2 - date of first study medication in Period 1 + 1) + 56.
 - ◆ Exposure in OLE = (date of last study medication in OLE - date of first study medication in OLE + 1) + 56.
 - For subjects on abatacept during Period 2, it is the sum of the following:
 - ◆ Exposure in Period 2 = (date of first study medication in OLE period - date of first study medication in Period 2) - adjustment. Adjustment is the period after 56 days from last study medication from Period 2 to the first study medication in OLE.
 - ◆ Exposure in OLE = (date of last study medication in OLE - date of first study medication in OLE + 1) + 56.
 - For subjects on abatacept during Period 2 and not entering OLE:
 - ◆ Exposure in Period 2 = (date of last study medication in Period 2 - date of first study medication in Period 2 + 1) + 56.

The offset of 56 days is the length of 2 regular dosing cycles and represents approximately 4 times the half-life of abatacept in humans.

Summaries of exposure to study drug will show the distribution of the number of infusions and days on drug, together with the means, standard deviations, medians, minima and maxima, by treatment group.

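### Appendix 2 item 7(b) states a single abstinence period, equal to the 100 days set for women of childbearing potential, and omits the 160 days that criterion 3(f) sets for males sexually active with them

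*Protocol*

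**What the plan says.** Protocol section 3.3.1, item 3, sets the periods after treatment by sex. Criterion 3(d) has WOCBP use contraception during treatment and for 5 half-lives (70 days) afterwards, "plus 30 days (duration of ovulatory cycle) for a total of 100 days post-treatment completion". Criterion 3(f) begins "Males who are sexually active with WOCBP must agree to follow instructions for method(s) of contraception" and sets the period as treatment "plus 5 half-lives of the study drug (70 days) plus 90 days (duration of sperm turnover) for a total of 160 days post-treatment completion". It adds that "male subjects must be willing to refrain from sperm donation during this time". Criterion 3(g) exempts azoospermic males and WOCBP who are continuously not heterosexually active. It has no matching exemption for abstinent males. Section 3.3.1 then tells investigators to counsel both WOCBP and males active with WOCBP, and points to Appendix 2 for the highly effective methods.

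Appendix 2 opens with "At a minimum, subjects must agree to use one highly effective method of contraception as listed below". The next paragraph expects WOCBP, and the WOCBP partners of male subjects, to use a method from the list, and states that "Male subjects must inform their female partners who are WOCBP of the contraceptive requirements of the protocol". Item 7 of the list is complete abstinence. Item 7(b) says that it "must be used throughout the duration of the study treatment (plus 5 half-lives of the investigational drug plus 30 days"). No other visible method in the list carries a duration for the trial, and item 7(b) gives no separate period for males.

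**The concern.** Section 3.3.1 sends sites to Appendix 2 when they counsel male subjects, and the list there applies to male subjects and their partners. The only length of use stated in the visible list is the one in item 7(b), and it is built from the 30-day ovulatory-cycle allowance. The protocol's own allowance for males is 90 days, for sperm turnover.

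At stake is the consistency of a safety instruction. Take a male whose method is abstinence and who becomes active with a WOCBP in the third to sixth month after treatment. A site reading item 7 alone could tell him that his obligation ended at day 100. A site reading 3(f) would say day 160. Item 7(e) requires other methods to be discussed when a subject gives up abstinence, but it does not say for how long they must be used.

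**Working it through.** **Inputs**
- 5 half-lives = 70 days (protocol 3.3.1, criteria 3(d) and 3(f)).
- Allowance for WOCBP = 30 days (3(d)); allowance for males = 90 days (3(f)).
- Item 7(b) = treatment + 5 half-lives + 30 days. It prints no total in days.
- SAP 7.4.1: the 56-day offset "represents approximately 4 times the half-life of abatacept in humans".

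**Step 1: check the half-life.** From the SAP, 56 / 4 = 14 days. From the protocol, 70 / 5 = 14 days. The two agree, so 70 days can be used in item 7(b).

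**Step 2: reproduce the stated totals.**
- 3(d): 70 + 30 = 100 days, as stated.
- 3(f): 70 + 90 = 160 days, as stated.

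**Step 3: put item 7(b) in days.** 70 + 30 = 100 days. This equals 3(d) and differs from 3(f).

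**Step 4: the gap.** 160 - 100 = 60 days, that is, days 101 to 160 after treatment completion. As a share of the male period, 60 / 160 = 37.5%.

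**Step 5: who falls in the gap.** Setting the texts side by side:
- A male already active with a WOCBP is plainly under 3(f): 160 days, no gap.
- A male who stays abstinent beyond day 160 has no exposure in the gap, whichever period is read.
- An azoospermic male is exempt under 3(g).
- A male whose method is abstinence and who becomes active with a WOCBP between days 101 and 160 gets 100 days from item 7(b) and 160 days from 3(f). This is the only group for whom the mismatch matters.

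**Step 6: would a visit catch it?** Table 5.1-4 places follow-up at 56, 84 and 168 days after the last dose, each ±14 days. Taking treatment completion as the last dose, the second visit is at latest day 84 + 14 = 98 and the third at earliest day 168 - 14 = 154. No target day lies within days 101 to 160, so the counselling has to be right beforehand.

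**The case against.** The best case against the point is that the two texts do not conflict. Criterion 3(f) is the numbered rule that the male accepts at entry. It states 160 days, and it applies by its own terms once he is active with a WOCBP. Section 3.3.1 refers to Appendix 2 for methods, not durations. Item 7 also looks drafted for women: item 7(d) requires pregnancy tests, and item 5(a) speaks of a WOCBP trial participant. On that reading, item 7(b) simply repeats 3(d). The Glossary and item 7(f) tie abstinence to the subject's usual lifestyle, and the Glossary refuses abstinence professed only to enter a trial, so few males should qualify.

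Most of this stands, and it limits the reach of the point. It does not remove the mismatch. The paragraph that assigns the list to women names the WOCBP partners of male subjects as well, so the list reaches those couples. A male who is abstinent when counselled is arguably outside 3(f) at that time, which leaves item 7(b) as the only visible period addressed to his method.

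A reader might infer three stronger things, and the documents support none of them:
- *That item 7(b) expressly fixes one period for all subjects.* Item 7(b) does not say so. The neighbouring phrase concerns all study drugs, and the reach to males comes from the appendix's introduction.
- *That the protocol shortens male contraception to 100 days.* Criterion 3(f) says 160 days and is the controlling text.
- *That no male abstinence period exists anywhere in the trial's materials.* Blacked-out blocks follow the list of unacceptable methods in Appendix 2, and the consent pages are not available. Neither can be counted as silent, although neither alters the visible words of item 7(b).

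**Conclusion.** The point holds as a narrow inconsistency of minor severity. Item 7(b) states only the female period, in a list that also serves male subjects and their partners. For the one group described above, the difference is 0 days if the site applies 3(f) and 60 days if it applies item 7 alone.

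The conclusion rests on two readings. Item 7(b) is taken to use the protocol's 70 days for 5 half-lives, which the SAP figure supports. The list is taken to reach male subjects, which follows from the introduction to Appendix 2 although item 7(b) does not say it. The documents give no count of affected males; that it is small is a judgement based on the usual-lifestyle condition.

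The point has no bearing on sample size, power, endpoints or analyses. Protocol section 6.4 requires a pregnancy in a male participant's partner to be reported whichever period a site has used.

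**What to change.** Amend item 7(b) so that the period after treatment reads:
- for WOCBP subjects, plus 5 half-lives plus 30 days (100 days), per 3.3.1 item 3(d);
- for male subjects who rely on abstinence from intercourse with WOCBP, other than azoospermic males exempt under 3(g), plus 5 half-lives plus 90 days (160 days), per 3.3.1 item 3(f).

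Add that a male who resumes intercourse with a WOCBP before day 160 must use another listed method until day 160. The limits in the second bullet matter: a flat 160 days for every male would go beyond 3(f) and ignore the 3(g) exemption.

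The cost is a short edit in the next protocol amendment and a check that the consent wording agrees. No visit, procedure or analysis is added.
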